**Comments**

(Include any held doses, or dose modifications)

#### 4.4.3 Treatment Details: All Subsequent Cycles

One cycle of XL184 treatment is described below. A cycle may be repeated every 28 days if the patient has at least stable disease and has again met laboratory parameters as defined in the eligibility [Section 3.2.7](#).

##### **XL184: PO**

Days: 1-28

Dose: 40 mg/m^2/day

Dosing will be performed based on body surface area (BSA), and rounded to the nearest 20 mg using the dosing nomogram (see [Appendix IV](#)). The cumulative weekly dose is 280 mg/m^2. Treatment will continue until tumor progression or unacceptable toxicity.

XL184 will be administered orally at approximately the same time each day as prescribed.

Drug doses should be adjusted based on the BSA calculated from height and actual body weight measured within 7 days prior to the beginning of each cycle, and according to the dosing nomogram (see [Appendix IV](#)). Sites will fill out the number of prescribed tablets per day in the patient diary (see [Appendix III](#)). Patients must complete the patient diary with the date, time and number of XL184 tablets taken each day. The patient diary should be reviewed after completion of each treatment cycle.

If a patient vomits after the dose of XL184 is administered, the dose should not be repeated. The tablet should be taken with a large glass of water on an empty stomach, and patient should not eat 2 hours before or 1 hour after each dose of XL184. The tablet should not be crushed or broken. Furthermore, a missed dose should not be taken within 12 hours of the next dose.

Patients should not eat grapefruit or drink grapefruit juice while being treated with XL184.

A note should be made in the patient diary if any of the above events take place.

See [Section 5.0](#) for Dose Modifications based on Toxicities.

Following completion of cycle, the next cycle starts on Day 29 or when starting criteria are met (see [Section 3.2.7](#)), whichever occurs later.

## 5.0 DEFINITIONS AND DOSE MODIFICATION FOR TOXICITY

All dose modifications should be based on the worst preceding toxicity. The severity of adverse events will be graded utilizing the NCI CTCAE, Version 5.0.

### 5.1 Definition of Dose-Limiting Toxicity (DLT)

DLT will be defined as any of the following events that are at least (possibly, probably or definitely) attributable to XL184.

Dose limiting hematological and non-hematological toxicities are defined differently.

#### 5.1.1 Non-Hematological Dose-Limiting Toxicity

- Any Grade 4 non-hematological toxicity
- Any Grade 3 non-hematological toxicity with the specific exception of:
  - Grade 3 nausea and vomiting of less < 3 days duration
  - Grade 3 diarrhea  $\leq$  3 days duration
  - Grade 3 liver enzyme elevation including ALT/AST/GGT/bilirubin that return to levels that meet initial eligibility criteria within 7 days of study drug interruption and that do not recur upon re-challenge with study drug. Note: For the purposes of this trial the ULN for ALT is defined as 45 U/L and the ULN for AST is defined as 50 U/L. See [Section 5.7](#) for dose modifications for liver toxicity. Adverse event grades will be based on increases above the upper limit of normal, regardless of the subject's baseline. See appendix XI for toxicity-specific grading table.
  - Grade 3 fever or infection < 5 days duration.
  - Grade 3 hypophosphatemia, hypokalemia, hypocalcemia and/or hypomagnesemia responsive to supplementation
  - Grade 3 asymptomatic amylase or lipase elevation that resolves to Grade 1 within 7 days of study drug interruption and that does not recur upon re-challenge with XL184. See [Section 5.8](#) for dose modifications for pancreatic toxicity.
  - Grade 3 proteinuria (urine protein/creatinine (P/C) ratio > 1.9) unless it is confirmed with a second measurement within 72 hours
- Any Grade 2 non-hematological toxicity that persists for  $\geq$  7 days and is considered sufficiently medically significant or sufficiently intolerable by patients that it requires treatment interruption
- Dose-limiting hypertension
  - Any Grade 4 hypertension
  - A blood pressure > 25 mmHg above the ULN confirmed by repeated measurement on the same day is dose limiting. For pediatric patients ULN is the 95th percentile for age, height, and gender ([Appendix V](#)) and for patients  $\geq$  18 years of age ULN is 140/90 mmHg.
  - In patients who begin antihypertensive therapy a blood pressure > 10 mmHg but  $\leq$  25 mmHg above the ULN ([Appendix V](#)) for > 14 days is dose limiting.
- QTc prolongation > 500 ms that persists despite correction of serum electrolyte abnormalities will be considered dose limiting

- Grade 2 or higher allergic reactions that necessitate discontinuation of study drug will not be considered a dose-limiting toxicity.

#### 5.1.2 Hematological dose limiting toxicity

- In patients evaluable for hematological toxicity (see [Section 3.2.7.1](#)),
  - Grade 4 thrombocytopenia (platelet count < 25,000/ $\mu$ L) or Grade 4 neutropenia, not due to malignant infiltration.
- Myelosuppression that causes a delay of > 21 days between treatment cycles.
- In patients with CNS tumors, requirement of platelet transfusion(s) for platelets  $\leq$  50,000/ $\text{mm}^3$  on more than one occasion during a cycle will be considered a DLT. If a patient with a CNS tumor requires more than one platelet transfusion to achieve a count > 50,000/ $\text{mm}^3$  (poor initial response, etc.) on one occasion this is not a DLT, but if it occurs again during the cycle, it will be dose limiting.

Note: Grade 4 febrile neutropenia will not be considered a dose-limiting toxicity.

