### 5.2 **Dose Modifications for Hematological Toxicity**

The Study Chair must be notified of any dosage modification or use of myeloid growth factor. If a patient's dose is reduced due to toxicity, any future XL184 total weekly dose should not exceed a dose that was previously not tolerated.

- 5.2.1 If a patient experiences Grade 4 neutropenia or Grade 4 thrombocytopenia, the treatment will be held. Counts should be checked twice weekly during this time. If the toxicity resolves to meet eligibility parameters within 21 days of drug discontinuation, the patient may resume treatment at the next lower dose level (see [Section 5.11](#)). Doses reduced for toxicity will not be re-escalated, even if there is minimal or no toxicity with the reduced dose.
- 5.2.2 If toxicity does not resolve to meet eligibility parameters within 21 days of drug discontinuation, the patient must be removed from protocol therapy.
- 5.2.3 Two dose reductions will be allowed for toxicity. If a patient experiences a dose limiting toxicity after two dose reductions, they must be removed from protocol therapy. For patients with BSA 0.35-0.39, only 1 dose reduction will be allowed as the lowest weekly administered dose is 60 mg/week.

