### 5.3 **Dose Modifications for Non-Hematological Toxicity**

- 5.3.1 XL184 will be discontinued in cases of serious toxicities such as GI perforation, fistula formation, significant bleeding, significant thrombotic events (such as myocardial infarction, cerebral infarction, other serious arterial thromboembolic events), Grade 4 hypertension, reversible posterior leukoencephalopathy syndrome, or osteonecrosis of the jaw. For other toxicities, if a patient experiences non-hematological dose-limiting toxicity as defined in [Section 5.1.1](#), the treatment will be held. When the toxicity resolves to meet eligibility parameters or baseline within 21 days of drug discontinuation, the patient may resume treatment at the next lower dose level (see [Section 5.11](#)). Doses reduced for toxicity will not be re-escalated, even if there is minimal or no toxicity with the reduced dose.

5.3.2 If toxicity does not resolve to meet eligibility or baseline parameters within 21 days of drug discontinuation, the patient must be removed from protocol therapy. The exception to this is Grade 3 weight loss as it is unlikely that the patient would return to baseline within 21 days. Patients who experience Grade 3 weight loss may resume study medication after 21 days with a dose-reduction (see [Section 5.11](#)) if the patient is deriving benefit from therapy, the weight loss has stabilized and the treating physician feels it is in the best interest of the patient. Patients should be removed from protocol therapy if their weight loss is  $\geq 20\%$  from baseline and persists for  $\geq 28$  days after the introduction of supplemental NG/G tube feeding or TPN.

5.3.3 Two dose reductions will be allowed for toxicity. If a patient experiences a dose limiting toxicity after two dose reductions, the patient must be removed from protocol therapy. For patients with BSA 0.35-0.39, only 1 dose reduction will be allowed as the lowest weekly administered dose is 60 mg/week.

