### 5.7 Dose Modifications for Liver Toxicity

XL184 should be held for Grade 3 elevation of ALT, AST or bilirubin. Note: For the purposes of this trial the ULN for ALT is defined as 45 U/L regardless of the patient's baseline, and the ULN for AST is defined as 50 U/L. XL184 may be re-administered at the same dose if levels of ALT, AST and bilirubin meet eligibility criteria or baseline within 7 days of drug discontinuation. Elevated laboratory parameters should be checked at least twice weekly until eligibility criteria are met.

If lab values do not resolve to initial eligibility criteria or baseline within 7 days of interruption or if toxicity recurs with re-challenge, then this will be considered dose-limiting per [Section 5.1.1](#). The XL184 will be reduced according to [Section 5.11](#) when eligibility criteria are met.

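### The repeat-platelet-transfusion DLT for CNS-tumor patients (Section 5.1.2) has no ordered hold or dose reduction when counts are 25,000–50,000

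*Combined protocol and SAP*

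**What the plan says.** Section 5.1 sets the attribution condition: "DLT will be defined as any of the following events that are at least (possibly, probably or definitely) attributable to XL184". Among the hematological events, 5.1.2 lists Grade 4 neutropenia, Grade 4 thrombocytopenia (a count below 25,000), myelosuppression that delays the next cycle by more than 21 days, and one rule specific to CNS tumors. Under that rule, platelet transfusion for a count of 50,000 or less "on more than one occasion during a cycle will be considered a DLT".

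The response to hematological toxicity is in Section 5.2. Section 5.2.1 begins: "If a patient experiences Grade 4 neutropenia or Grade 4 thrombocytopenia, the treatment will be held". It then asks for twice-weekly counts and allows resumption at the next lower level if the counts recover to eligibility limits within 21 days. Section 5.2.2 removes patients who do not recover in that time. Section 5.2.3 adds: "If a patient experiences a dose limiting toxicity after two dose reductions, they must be removed from protocol therapy". For the smallest patients it adds: "For patients with BSA 0.35-0.39, only 1 dose reduction will be allowed as the lowest weekly administered dose is 60 mg/week".

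**The concern.** The CNS rule uses a higher platelet threshold than the Grade 4 cut-off, so it flags these patients earlier. Section 5.2.1 responds only at Grade 4. Between 25,000 and 50,000 the event is therefore called dose-limiting, yet nothing tells the site to change the dose.

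At stake is the handling of individual patients. A patient with an at least possibly drug-related DLT may stay on the same dose, and does not get the twice-weekly counts that accompany a hold under 5.2.1. The scheduled blood counts are every two weeks in Cycles 1–3 and only on Day 1 of later cycles (Sections 4.2.2, 4.3.2, 4.4.2). One investigator may reduce on judgment while another follows 5.2.1 literally, so sites may treat the same event differently.

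The plan is also uneven within itself: after two reductions the same event forces removal from therapy, whereas at full dose or the first reduced level it orders nothing.

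**Working it through.** There is no planned figure to reproduce. The check takes a CNS-tumor patient with two transfusion occasions in one cycle, counts of 25,000–50,000, and at least possible attribution, and compares that case with every clause that could order an action.

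| Clause | What it does | Orders a hold or reduction here? |
|---|---|---|
| 5.0, opening | "All dose modifications should be based on the worst preceding toxicity" – says which toxicity governs a modification | No |
| 4.1.1 | Permits reductions for toxicities, referring back to Section 5.0 | No, permissive only |
| 5.2.1 | Hold, then next lower level, for the two Grade 4 events | No, count is not below 25,000 |
| 5.2.2 | Removal if not recovered 21 days after stopping drug | No, presupposes a hold |
| 5.2.3 | Removal for a DLT after two reductions | No, and this event generates no reductions |
| 5.3.1 | Applies "if a patient experiences non-hematological dose-limiting toxicity as defined in" Section 5.1.1 | No, wrong class of DLT |
| 5.4–5.10 | Specific non-hematological toxicities | No |
| 5.11 | Dose levels only | No |
| 4.1.3 with 3.2.7 | Laboratory requirements for starting a cycle | No, may delay the start but leaves the dose unchanged |
| 8.1(e) | Removal at the physician's discretion | No |

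The cycle-start requirement is 100,000 or more with no platelet transfusion in the previous 7 days, or 50,000 or more with transfusion allowed when there is known marrow disease. It applies to everyone, whether or not a DLT occurred.

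Other sections show the usual pattern. For liver enzymes that do not recover in time or recur on re-challenge, 5.7 says "The XL184 will be reduced according to" Section 5.11. Sections 5.8 and 5.9 also order a reduction, and 5.10.2 sends its DLT to 5.3.

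**Size of the reduction not ordered** (weekly mg, 13 BSA bands in order).
- Initial dose, Appendix IV: 100, 120, 140, 160, 200, 240, 280, 300, 360, 420, 480, 560, 600.
- First reduction, 5.11: 60, 80, 100, 120, 140, 160, 200, 200, 240, 300, 360, 420, 420.
- Second reduction, 5.11: off therapy, 60, 60, 80, 100, 120, 140, 140, 160, 200, 240, 300, 300.

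First step ÷ initial: lowest 60/100 = 0.60; highest 120/160 = 360/480 = 420/560 = 0.75.

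Second step ÷ initial (12 bands): lowest 60/140 = 0.43; highest 300/560 = 0.54.

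**Context from the pediatric phase 1 trial (2.4.1).** Enrollment was 5+2+4+2+4+2+2+2+3+9+6 = 41, of whom 9 had CNS tumors (9/41 = 22%). None of the 10 listed Cycle 1 DLT types is hematological, although thrombocytopenia was among the most frequent adverse events. That trial's DLT definition and eligibility criteria are not given here, so these figures do not predict how many patients this trial would see.

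**The case against.** The strongest case is that this is a rare drafting slip with little room for harm.

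- **Rarity.** Many conditions must coincide: a CNS tumor with a documented target alteration, two transfusion occasions in one cycle, at least possible attribution, counts never below 25,000, and fewer than two earlier reductions.
- **Short exposure.** A second occasion in one cycle will usually come to light through unscheduled counts, so the patient is already being actively managed. Without marrow disease, the next cycle cannot start until platelets reach 100,000 unsupported, and a delay of more than 21 days is itself a DLT.
- **Other safeguards.** Section 4.1.1 permits a reduction. Thrombocytopenia is on the list for the Bayesian toxicity rule in 9.3.4, evaluated at least monthly, and Grade 3 and higher events are routinely reported under 11.10.
- **Uneven pattern elsewhere.** Section 5.6 holds drug for a venous clot but makes the later reduction optional, and the 21-day-delay DLT is not named in 5.2.1 either.

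The rarity stands and limits the importance of the point. The comparison with other sections is a tendency, not a universal rule. The delay DLT differs because drug has already been withheld, and 5.2.2 then removes the patient if recovery fails. The remaining points do not fill the gap: the cycle-start requirement does not stop dosing within a cycle or lower the dose afterward, a permission is not an instruction, and the Bayesian rule sends an aggregate signal to the monitoring committee without changing one patient's dose.

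**Conclusion.** The gap is real. It covers counts of 25,000–50,000, events at least possibly attributable to XL184, and patients with fewer than two earlier reductions. At BSA 0.35–0.39 it covers only patients with no earlier reduction; that reading is inferred from the one-reduction limit and the off-therapy entry in 5.11, since 5.2.3 states removal only after two.

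The number affected is not stated in the documents and must be very small. The response and disease-control endpoints and their decision rules are untouched. That this is an oversight, not a deliberate choice, is an inference from the jump between no action and removal and from the way most other DLTs are handled; the documents do not state the intent. It should be corrected as a patient-safety matter, and it does not threaten the trial's conclusions.

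**What to change.** In the trigger sentence of 5.2.1, add a third event after the two Grade 4 events: for patients with CNS tumors, the platelet-transfusion DLT defined in 5.1.2. The existing hold, twice-weekly counts, 21-day recovery limit and resumption at the next lower level in 5.11 then apply without further drafting. Name only this event. Extending the trigger to every DLT in 5.1.2 would bring in the more-than-21-day-delay DLT, which conflicts with the 21-day recovery window.

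The cost is one sentence at the next amendment and no extra patients. An affected patient would have up to about 2 × 3 = 6 counts during a 21-day hold. The real downside is lower dose intensity, 60–75% of the full weekly dose at the first step with no re-escalation, in patients who may have few alternatives. With known marrow disease the hold could be brief, because a transfusion-supported count of 50,000 already meets the recovery limit; the lower dose on resumption would still apply.

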### 5.2 **Dose Modifications for Hematological Toxicity**

The Study Chair must be notified of any dosage modification or use of myeloid growth factor. If a patient's dose is reduced due to toxicity, any future XL184 total weekly dose should not exceed a dose that was previously not tolerated.

- 5.2.1 If a patient experiences Grade 4 neutropenia or Grade 4 thrombocytopenia, the treatment will be held. Counts should be checked twice weekly during this time. If the toxicity resolves to meet eligibility parameters within 21 days of drug discontinuation, the patient may resume treatment at the next lower dose level (see [Section 5.11](#)). Doses reduced for toxicity will not be re-escalated, even if there is minimal or no toxicity with the reduced dose.
- 5.2.2 If toxicity does not resolve to meet eligibility parameters within 21 days of drug discontinuation, the patient must be removed from protocol therapy.
- 5.2.3 Two dose reductions will be allowed for toxicity. If a patient experiences a dose limiting toxicity after two dose reductions, they must be removed from protocol therapy. For patients with BSA 0.35-0.39, only 1 dose reduction will be allowed as the lowest weekly administered dose is 60 mg/week.

### 5.3 **Dose Modifications for Non-Hematological Toxicity**

- 5.3.1 XL184 will be discontinued in cases of serious toxicities such as GI perforation, fistula formation, significant bleeding, significant thrombotic events (such as myocardial infarction, cerebral infarction, other serious arterial thromboembolic events), Grade 4 hypertension, reversible posterior leukoencephalopathy syndrome, or osteonecrosis of the jaw. For other toxicities, if a patient experiences non-hematological dose-limiting toxicity as defined in [Section 5.1.1](#), the treatment will be held. When the toxicity resolves to meet eligibility parameters or baseline within 21 days of drug discontinuation, the patient may resume treatment at the next lower dose level (see [Section 5.11](#)). Doses reduced for toxicity will not be re-escalated, even if there is minimal or no toxicity with the reduced dose.

5.3.2 If toxicity does not resolve to meet eligibility or baseline parameters within 21 days of drug discontinuation, the patient must be removed from protocol therapy. The exception to this is Grade 3 weight loss as it is unlikely that the patient would return to baseline within 21 days. Patients who experience Grade 3 weight loss may resume study medication after 21 days with a dose-reduction (see [Section 5.11](#)) if the patient is deriving benefit from therapy, the weight loss has stabilized and the treating physician feels it is in the best interest of the patient. Patients should be removed from protocol therapy if their weight loss is  $\geq 20\%$  from baseline and persists for  $\geq 28$  days after the introduction of supplemental NG/G tube feeding or TPN.

5.3.3 Two dose reductions will be allowed for toxicity. If a patient experiences a dose limiting toxicity after two dose reductions, the patient must be removed from protocol therapy. For patients with BSA 0.35-0.39, only 1 dose reduction will be allowed as the lowest weekly administered dose is 60 mg/week.

#### 5.4 Dose Modifications for Proteinuria

Proteinuria has been reported with XL184 in adult studies and pediatric trial ADVL1211.

[figure not shown]
- If urinalysis shows  $\geq$  trace protein then obtain UPC.
- If the urine protein/creatinine (P/C) ratio  $\leq 1.9$  continue XL184. If patient has Grade 3 proteinuria (urine protein/creatinine (P/C) ratio  $> 1.9$ ), a second measurement should be obtained within 72 hours. A second confirmation of Grade 3 proteinuria will be considered a DLT.
- If the second measurement confirms Grade 3 proteinuria (urine protein/creatinine (P/C) ratio  $> 1.9$ ), then interrupt XL184 treatment and re-assess weekly.
- If XL184 is held for  $\geq 21$  days then remove from protocol therapy. If the urine protein/creatinine (P/C) ratio decreases to  $\leq 1.9$  in  $< 21$  days then resume XL184 at a lower dose as outlined in [Section 5.11](#).
- Monitor the UPC weekly for 2 consecutive weeks once protocol therapy resumes.

#### 5.5 Dose Modifications for Hypertension

- **Baseline blood pressure (BP)** is defined as the blood pressure obtained at the examination used for study enrollment. This baseline BP should be obtained as follows: 1) Obtain 3 serial blood pressures from the same extremity with the patient in the same position at rest with an appropriately sized cuff that are separated by at least 5 minutes. Avoid using the lower extremity if possible. 2) Average the systolic blood pressure from the 2nd and 3rd measurements. 3) Average the diastolic blood pressure from the 2nd and 3rd measurements. 4) The baseline BP is the average of the systolic over the average of the diastolic measurements.
- **Elevation** in either the systolic or diastolic blood pressure should be considered when following the algorithm below.
- **The (ULN)** is defined as a BP equal to the 95th percentile for age, height, and gender for pediatric patients (See [Appendix V](#)) For adult patients (ages  $\geq 18$  years), the ULN is 140/90 mmHg.
- The NCI CTCAE will be utilized to determine the grade of hypertension for reporting purposes.
- Elevated BP measurements should be repeated on the same day to confirm the elevation. If confirmed, patients with elevated BP should have BP measurements performed at least twice weekly until BP is  $\leq$  ULN.
- The algorithm below will be used to manage XL184- related hypertension.

- Hypertension should be managed with appropriate anti-hypertensive agent(s) as clinically indicated. It is strongly recommended that nephrology or cardiology be consulted in the evaluation and management of hypertension.

Elevations in BP are based on systolic or diastolic pressures.

 Elevated blood pressure (BP) measurements should be repeated on the same day to confirm the elevation. Patients with elevated BP at any time should have BP measurements performed at least twice weekly until BP within the ULN (Upper Limit of Normal).

 ULN for pediatric patients is a BP equal to the 95th percentile for a age, height, and gender-appropriate normal values (see [Appendix V](#)). For adult patients (ages ≥ 18 years) the ULN is 140/90 mmHg.

 If BP > 25 mm Hg above ULN for age (verified) or Grade 4 HTN at any time, hold drug. Study drug should also be held for BP ≤ 25 mm Hg above the ULN age for > 14 days or 35 mm Hg above baseline for > 14 days. Antihypertensive agents can be used to control hypertension as clinically indicated after study drug is held.

 Anti-hypertensive therapy should be prescribed as clinically indicated, including the use of multiple anti-hypertensive agents.

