### 3.2.7.6 Adequate Blood Pressure Control defined as:

A blood pressure (BP)  $\leq$  the 95th percentile for age, height, and gender for pediatric patients < 18 years old ([Appendix V](#)) and  $\leq$  140/90 mmHg for patients  $\geq$  18 years old. BP should be measured as described in [Section 5.5](#), and patients should not be receiving medication for treatment of hypertension (except patients with Wilms tumor and RCC who may be eligible if on stable doses of no more than one anti-hypertensive medication with a baseline BP  $\leq$  ULN for pediatric patients and  $\leq$  140/90 for adult patients). Please note that 3 serial blood pressures should be obtained and averaged to determine baseline BP.

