**Arm 5 of algorithm:**

- If the participant develops Grade 4 hypertension, **discontinue** XL184, monitor BP and administer anti-hypertensive therapy as clinically indicated. The patient is Off Protocol Therapy.

**Should initiation of anti-hypertensive therapy be required, single agent therapy (commonly including the calcium channel blockers amlodipine or nifedipine, which are permissible without discussion with the study chair) should be started and the blood pressure should be monitored at least twice weekly until BP is  $<$  ULN.**

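### The blood pressure rules disagree on Grade 4 hypertension, on hold and reduction triggers, and on how baseline BP is calculated

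*Combined protocol and SAP*

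**What the plan says.** All references are to the combined protocol and SAP.

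- **Grade 4 hypertension.** Section 5.5, footnote 3: "or Grade 4 HTN at any time, hold drug". The same sentence covers a verified BP more than 25 mm Hg above ULN. Section 5.5, Arm 5: "If the participant develops Grade 4 hypertension, discontinue XL184", with the patient then off protocol therapy. Section 5.3.1 lists "Grade 4 hypertension, reversible posterior leukoencephalopathy syndrome, or osteonecrosis of the jaw" among the toxicities for which the drug is discontinued.
- **Persistent elevation.** Section 5.1.1 has a DLT criterion that opens "In patients who begin antihypertensive therapy a blood pressure" and covers values more than 10 and up to 25 mm Hg above ULN lasting more than 14 days. Section 5.5, footnote 3, adds: "Study drug should also be held for BP" up to 25 mm Hg above ULN, or 35 mm Hg above baseline, in each case for more than 14 days. Arm 2 sends elevations of 10 mm Hg or less that persist on recheck into Arm 3. Arm 3 holds drug after 14 days on antihypertensive therapy and restarts it at a reduced dose if BP comes back within ULN.
- **Baseline BP.** Section 3.2.7.6: "3 serial blood pressures should be obtained and averaged to determine baseline BP". Section 5.5 also takes three readings but then says "Average the systolic blood pressure from the" second and third measurements, and does the same for diastolic pressure.

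**The concern.** Section 2.4.1 reports hypertension as a cycle 1 DLT and one of the most frequent adverse events in the paediatric phase 1 trial, so sites should expect to use these rules. As written, two sites could handle the same Grade 4 event differently, with one interrupting drug and the other ending protocol therapy. A patient can have the dose reduced for an elevation below the hypertension-specific DLT threshold, while the rule for removal after two reductions is tied to a DLT. Baseline BP feeds both an inclusion criterion, which Section 3.2 says is applied literally and without waiver, and the 35 mm Hg trigger in Section 5.5. Eligibility, drug interruption, time on therapy and DLT classification are therefore all open to site interpretation.

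**Working it through.** The plan gives no figure to reproduce. The check sets the texts side by side, with short arithmetic where a threshold or formula is involved.

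**1. Grade 4 hypertension**

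- Footnote 3: hold, paired with BP more than 25 mm Hg above ULN.
- Arm 4, for BP more than 25 mm Hg above ULN: hold, with restart at a reduced dose allowed if BP is within ULN in 14 days.
- Arm 5: discontinue, off protocol therapy.
- Section 5.3.1: discontinue. The same section then says that for other toxicities a DLT leads to a hold with possible resumption, so it treats holding and discontinuing as different actions.

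Footnote 3 therefore places Grade 4 hypertension with an elevation that can be restarted; Arm 5 and Section 5.3.1 place it with events that end treatment.

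**2. Triggers and the DLT definition**

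*Threshold.* Take BP 5 mm Hg above ULN for 15 days on antihypertensive therapy. Section 5.1.1 persistent-hypertension criterion: 5 is not above 10, so it is not met. Arms 2 and 3: 5 is within 25 and 15 days exceeds 14, so drug is held, then restarted at a reduced dose if BP returns to ULN or below within 14 days.

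*After two reductions.* Section 5.3.3 allows two reductions and states removal for a DLT occurring after them. The Section 5.11 table has no third level (for BSA 0.35–0.39 the second column already reads off therapy). A patient at the second level who meets the Arm 3 hold without a DLT is directed to a further reduced dose that the table does not contain.

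*Clock.* Suppose BP is first elevated on day 0, is confirmed at the 72-hour recheck, and therapy starts on day 3. Footnote 3 counts the elevation itself, so its 14 days end on day 14. Arm 3 counts from the start of antihypertensive therapy, so its 14 days end on day 3 + 14 = 17. The gap is 3 days in this example.

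*Rise over baseline.* Arm 1 says continue at the same dose if BP is at or below ULN. For an adult with systolic ULN 140, a rise of 35 stays within ULN whenever baseline is 140 − 35 = 105 or lower. Illustration with assumed values: baseline 100, sustained 138, diastolic normal. The rise is 138 − 100 = 38, so footnote 3 holds after 14 days; 138 is within 140, so Arm 1 continues. The baseline trigger does not appear in Section 5.1.1.

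**3. Baseline BP**

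Let *a* be the first reading and *m* the mean of the second and third.

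- Section 3.2.7.6: (*a* + 2*m*)/3.
- Section 5.5: *m*.
- Difference: (*a* + 2*m*)/3 − *m* = (*a* − *m*)/3.

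The documents give no typical value of *a* − *m*, so these gaps are assumed:

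| Assumed gap *a* − *m* (mm Hg) | Difference in baseline (mm Hg) |
|---|---|
| 3 | 1 |
| 6 | 2 |
| 9 | 3 |
| 12 | 4 |

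A first reading lower than the others reverses the sign. Eligibility example with assumed adult systolic readings 148, 138, 136: all three give 422/3 = 140.7, above the 140 limit; the last two give 274/2 = 137.0, within it. For patients who do enrol, the 35 mm Hg trigger moves by the same one third of the gap.

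**The case against.** **Grade 4.** Holding can be the first step before discontinuation. Footnote 3 says nothing about restarting, and the chart it annotates is not reproduced in the text available for review. Arm 5 and Section 5.3.1 agree with each other. This narrows the conflict to one footnote but does not remove it: the footnote pairs Grade 4 with a restartable elevation and never mentions discontinuation.

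**DLT definition.** A reader might infer that the plan holds two competing DLT definitions. It does not. Section 5.5 never calls anything dose limiting, and Appendix V refers to Section 5.1.1 for that definition and to Section 5.5 for management and grading. Nor is it established that every reduction for a 1–10 mm Hg elevation occurs without a DLT. Another Section 5.1.1 bullet makes some persistent Grade 2 toxicities that require interruption dose limiting, and the documents do not reproduce the CTCAE grades needed to apply it. Holding drug before a toxicity counts as dose limiting also occurs in Sections 5.7 and 5.8, although there the reduction follows the DLT.

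**Continuing drug.** A reader might also infer that sites could continue drug in Grade 4 hypertension or through a persistent 1–10 mm Hg elevation. No passage says so; Arms 2 and 3 and footnote 3 all lead to a hold for the latter. The conflict between hold and continue is confined to a BP within ULN but far above baseline.

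**Baseline.** Section 3.2.7.6 refers to Section 5.5 for measurement, so its sentence on averaging may be shorthand for the Section 5.5 procedure. That is a fair reading, but the literal wording differs in a criterion that is to be read literally.

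**Conclusion.** The blood pressure rules are internally inconsistent in three places: the action for Grade 4 hypertension; the hold and reduction triggers, which match neither the DLT criterion and removal rule nor each other; and the baseline BP formula. The second is a mismatch of thresholds and clocks.

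The first two can change whether and when a patient is held, reduced or taken off therapy. The third changes baseline by one third of the first-reading gap, which is 1 to 4 mm Hg for the assumed gaps of 3 to 12 mm Hg. That matters only near the eligibility limit and for the 35 mm Hg trigger. How often any of this would arise cannot be computed from the documents.

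A reader might carry the point over to the efficacy results or to the Section 9.3.4 monitoring rule. The documents do not support that. The response-rate designs and their error rates do not use these rules, and Section 9.3.4 lists hypertension but counts toxicity events per cycle without reference to DLT status, holds or baseline BP. The effect is on safety management, eligibility and DLT classification, which is enough to justify a correction.

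**What to change.** In an amendment:

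- Reconcile footnote 3 of Section 5.5 with Arm 5 and Section 5.3.1, so that Grade 4 hypertension has one instruction.
- Align the Arm 1, Arm 3 and footnote 3 triggers and 14-day clocks with each other and with Sections 5.1.1 and 5.3.3. State what happens when a hold is triggered at the last level in Section 5.11 without a DLT, and how the rise-over-baseline trigger applies when BP is within ULN.
- Use one baseline BP formula in Sections 3.2.7.6 and 5.5.

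The clinical team must decide which version stands in each case; this review does not propose one. The cost is wording only, with no added procedures and no change to sample size or analysis.
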